Dose Level	Copanlisib Dose/Schedule
0	60 mg IV weekly
-1	45 mg IV weekly

Table 11-8: Dose modification for copanlisib-related nonhematological toxicity (except

glucose increases, dermatologic toxicity, noninfectious pneumonitis, and blood pressure increases)

Toxicity ^a	Occurrence	For current course of therapy	For next course of therapy
Grade 1-2	Any appearance	No change	No change
Grade 1b	1 st appearance	Delay until grade 3;2	No change
	2 nd appearance	Delay until grade 3;2	Decrease by 1 dose level ^c
	3 rd appearance	Permanently discontinue	
Grade 4	Any appearance	Permanently discontinue	
!Toxicity requiring delay for >21 days		Permanently discontinue	

^aToxicities according to CTCAE version 5.0.

^bDespite maximum supportive therapy.

^cNot applicable for 45-mg dose level.

Table 11-9: Dose modification for copanlisib-related hematologic toxicity

Hematological toxicity (any of the following)	Study treatment action (for any toxicity)

 CTCAE grade 3 thrombocytopenia (platelet<50,000/mm³) Febrile neutropenia CTCAE grade 3 neutropenia (ANC <1000/mm³) INR or PTT CTCAE grade 3 with bleeding^a CTCAE grade 3 anemia (Hb <8 g/dl) 	Delay infusion until Hgb 8, platelets 75, and ANC 1500/m m ³ without fever. ^b Patient can be treated at 1 dose level lower, at the investigator's discretion. If more dose reductions are required than are allowed per the protocol, discontinue copanlisib permanently.

ANC = absolute neutrophil count; Hb = hemoglobin; INR = international normalized ratio; PTT = partial thromboplastin time.

^aINR and PTT should have returned to ≤1.5 and ≤1.5 x ULN, respectively, with no signs of bleeding.

^bMer full recovery from toxicity and in the absence of any criteria for further dose reduction or study drug discontinuation, re-escalation to dose level -1 or 1 is allowed, at the investigator's discretion.

^cTreatment with transfusion or growth factors is allowed, at the investigator's discretion.

Table 11-10: Dose modification for copanlisib-related dermatologic toxicity

Toxicity ^a	Occurrence	For current course of therapy	For next course of therapy
Grade 1	Any appearance	No change	No change
Grade 2 ^b	1 st appearance	Interruption until grade 3;1	No change
	2 nd appearance	Interruption until grade 3;1	Decrease by one dose level ^c
	3 rd appearance	Permanent discontinuation	
Grade 3b	1 st appearance	Interruption until grade 3;1	Decrease by one dose level ^c
	2 nd appearance	Permanent discontinuation	

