Grade 4	pt appearance	Permanent discontinuation	

^aToxicities according to CTCAE version 5.0.

^bDespite maximum supportive therapy.

^cNot applicable for 45-mg dose level.

The lowest dose level is 45 mg; if a patient is already at the 45-mg dose level and meets criteria for a further decrease of dose, the study drug will be discontinued permanently.

Recommendations for Non-infectious Pneumonitis (NIP)

In the event of suspected NIP of any grade, copanlisib must be interrupted and diagnostic examination of the patient experiencing pulmonary symptoms conducted. If NIP is the final diagnosis, copanlisib must be permanently discontinued if CTC grade 3. For CTC grade 2, the patient should be treated until resolution or improvement to CTC grade 1; the next lower dose level of copanlisib should then be given. Pneumonitis is to be reported as such only in the event of NIP. If NIP related to copanlisib is confirmed, the treating investigator should administer systemic steroids.

The investigator is requested to differentiate between NIP and infectious pneumonitis (viral, bacterial, fungal), aspiration pneumonitis, or other pneumonitis clearly not due to a potential hypersensitivity reaction to the copanlisib infusion; the investigator must provide the basis for their assessment of infectious or other diagnosis, as appropriate. The investigator is requested to use the most-specific clinical terms to describe the condition in their report, not simply "pneumonitis."

Table 11-11: Dose adjustment in cases of NIP

Suspected or confirmed NIP per CTCAE		Action Taken	Retreatment dose after recovery
Grade 1		No change	NA
Grade 2		Dose interruption until recovery to grade ::,1	Decrease dose to the next lowest dose level ^a
Grade 2 second re-occurrence		Permanent discontinuation	NA
Grade 3		Permanent discontinuation	NA
Grade 4		Permanent discontinuation	NA

NA= Not applicable.

aNot applicable for 45-mg dose level. No re-escalation is allowed after the dose reduction.

The lowest dose level is 45 mg; if the patient is already at the 45-mg dose level and cannot tolerate treatment, the study treatment will be discontinued permanently.

Recommendations for arterial hypertension

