In the event of arterial hypertension 150/90 mmHg during infusion of copanlisib during any cycle, antihypertensive treatment is suggested, as indicated in Table 8. In the event of CTCAE grade 3 arterial hypertension (160/100 mmHg) during infusion of copanlisib, the infusion should be interrupted and antihypertensive treatment administered, as suggested above. Infusion can be resumed when blood pressure has returned to <150/90 mmHg.

Table 11-12: Dose modification for copanlisib-related arterial hypertension

Toxicity (CTCAE)	Study drug action	Recommendation
Predose measurements Blood pressure 150/90 mmHg	No dose should be given until recovery to <150/90mmHg.	Blood pressure-lowering medication should be considered. Dosing can proceed on the scheduled day if 2 consecutive measurements <150/90 mmHg are recorded. If blood pressure doesn't return to <150/90 mmHg, delay dosing until the next visit.
During infusion: CTCAE hypertension of grade 3 or 160/100 mmHg	Infusion can be interrupted or slowed down, and administration of blood pressure--lowering therapy should be initiated.	Infusion maybe resumed when blood pressure has returned to <150/90 mmHg, at the investigator's discretion, or it can be skipped. Subsequent study drug administrations maybe reduced by 1 dose level, at the investigator's discretion.b
Postdose: Drug-related CTCAE hypertension of grade 3 or 160/100 mmHg^a		Administration of blood pressure-lowering therapy should be initiated, in accordance with the local standard of care. Additional measurements to be performed as clinically indicated until recovery to <150/90mmHg. Subsequent study drug administrations maybe reduced by 1 dose level, at the investigator's discretion.b
CTCAE hypertension of grade 4	Permanently discontinue study drug.	

^aNot manageable despite optimal antihypertensive treatment.

bThe lowest dose level is 30 mg.

Table 11-13 Management of copanlisib-related infusion-related hyperglycemia

Criteria	Recommendation	Suggested Treatment
A5 asymptomatic glucose increase >250 mg/dl (13.9 mmol/L)	Does not generally require treatment with glucose-lowering medication	Oral hydration
A5 asymptomatic glucose increase >250 mg/dl (13.9 mmol/L)	
 • Repeat glucose testing • If glucose value is decreasing, glucose levels may be followed without glucose-lowering medication treatment if hydration status is normal, as clinically assessed 	Oral and/or IV hydration as appropriate

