	
 Consultation with endocrinologist can be considered 	
Symptomatic or persisting glucose increase >250 mg/dl (13.9 mmol/L)	
 Hydration status should be clinically assessed If clinical assessment is consistent with dehydration, fluids should be given as clinically appropriate (orally or IV) Laboratory test confirming increase should be repeated. If the repeated glucose value is persistent and/or the patient is symptomatic and/or the hydration status indicates the need for hydration, glucose-lowering medication should be administered Prompt input from an endocrinologist should be obtained 	
 Keep well-hydrated. Rapid/short-acting insulin maybe given if glucose persisting at >250 mg/dl (13.9 mmol/L) and the patient is symptomatic 
Rapid/short-acting insulin, according to the institution's sliding scale coverage of glucose persisting at >250 mg/dl (13.9 mmol/L), is recommended, with oral or IV hydration, as clinically appropriate

Asymptomatic glucose increase >500 mg/dl	
 Will require dose reduction for subsequent treatment infusion Repeat glucose testing If glucose value is decreasing, glucose levels may be followed without glucose-lowering medication treatment, if hydration status is normal, as clinically assessed Consultation with endocrinologist is recommended 	
 Keep well-hydrated. Rapid/short-acting insulin maybe given if glucose persisting at >250 mg/dl (13.9 mmol/L) and the patient is symptomatic For insulin-naive patients, monitor for signs of hypoglycemia 3 h after insulin administration due to risk for hypoglycemic events
Persistent glucose >200 mg/dl (11.1 mmol/L) nonfasting or >160 mg/dl (8.9 mmol/L) fasting postinfusion	
 Oral glucose-lowering medications and consultation with endocrinologist can be considered 	
 The use of sulphonylurea/metformin, insulin secretagogues medications to manage increased glucose levels following drug infusions is not recommended Treatment with glucose-lowering medication is suggested, in accordance with the local standards of practice

Treatment of copanlisib-related vomiting and diarrhea

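### Section 11.2 gives contradictory copanlisib instructions on the lowest dose level (45 mg or 30 mg) and on suspected grade 1 pneumonitis (interrupt or no change)

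*Combined protocol and SAP*

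**What the plan says.** **Lowest copanlisib level.** Table 11-7 sets the ladder for copanlisib-related adverse events in general. It has two rows: level 0 at 60 mg and level -1 at "45 mg IV weekly". Footnotes to Tables 11-8, 11-10 and 11-11 say that a decrease is not "applicable for 45-mg dose level". The text after Table 11-10 reads "The lowest dose level is 45 mg; if a patient is already at the 45-mg dose level and meets criteria for a further decrease" and goes on to require permanent discontinuation. The text after Table 11-11 repeats the 45-mg floor and adds: "if the patient is already at the 45-mg dose level and cannot tolerate treatment, the study treatment will be discontinued permanently".

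Table 11-12 covers copanlisib-related hypertension. For grade 3 events during or after the infusion it allows later doses to be cut by one level, at the investigator's discretion. Footnote b, attached to that reduction, says the "lowest dose level is 30 mg".

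**Suspected grade 1 NIP.** The NIP recommendations say: "In the event of suspected NIP of any grade, copanlisib must be interrupted", with a diagnostic work-up. Table 11-11, directly below, is headed as applying to suspected or confirmed NIP. Its grade 1 row gives no change as the action and no retreatment dose.

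**Status of these rules.** The opening of the dose-modification guidance in Section 11.2 calls the recommendations general guidelines. It lets the treating investigator consider a reduction or delay for any event, for safety reasons.

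**The concern.** These are instructions that site staff act on during treatment, and on both points the printed rules lead to opposite actions. An investigator whose patient is on copanlisib 45 mg and has grade 3 hypertension finds a lower level in one place. Elsewhere the same section has no lower level and requires permanent discontinuation. An investigator who suspects grade 1 NIP is told in the text to interrupt and in the table to change nothing.

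The first conflict is not confined to a rarely used dose, because the trial starts at copanlisib 45 mg. The second concerns the only event that Section 17.2.1 lists as being of special safety interest, to be reported to the copanlisib supplier within 24 hours. Two patients with the same event could be managed differently, each according to the protocol. Section 9.2 also relies on the Section 11 modification rules when it lets a patient continue at a lower dose after a DLT, so the ladder it points to should be unambiguous.

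**Working it through.** No calculation applies. The check compares every statement of the floor dose and both statements on suspected grade 1 NIP.

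**1. Lowest copanlisib level in Section 11.2**

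| Place | Lowest level | How it is given |
|---|---|---|
| Table 11-7 (general ladder) | 45 mg | by effect: last row |
| Table 11-8, footnote c | 45 mg | by effect |
| Table 11-10, footnote c | 45 mg | by effect |
| Sentence after Table 11-10 | 45 mg | in words |
| Table 11-11, footnote a | 45 mg | by effect |
| Sentence after Table 11-11 | 45 mg | in words |
| Table 11-12, footnote b | 30 mg | in words |

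For 45 mg: 2 in words + 4 by effect = 6 places. For 30 mg: 1 place. This counts places in the text, not patients, and it does not show which figure is intended.

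**2. Can it arise at the starting dose?** Table 9-1 gives copanlisib 45 mg at level 1 (the start), level -1 and level -2, and 60 mg only at level 2. That is 3 of 4 levels. A patient on any of the three is already at the bottom of Table 11-7, so a one-level reduction under Table 11-12 has no target in that ladder, yet footnote b says that one exists.

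**3. Suspected grade 1 NIP**

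| Source | Scope | Action at grade 1 |
|---|---|---|
| NIP text | suspected, any grade | interrupt (mandatory wording) |
| Table 11-11 | suspected or confirmed | no change |

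The two overlap exactly at suspected grade 1, where the actions differ. The text gives no separate action for confirmed grade 1, so the conflict lies mainly in the work-up period.

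**4. Reach.** Section 4.2 plans two copanlisib doses, and Section 9.1 puts them on treatment days 8 and 15. Under footnote c to Table 10-2, only patients going on to I-131 receive the second. A floor on later doses therefore matters only after the first infusion. The NIP conflict bears mainly on whether a patient under work-up receives the second infusion as scheduled. Footnote e to Table 10-2 also mentions a third infusion, but Section 4.2 plans none.

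**5. Damage from text extraction.** Comparison signs are missing in several of these tables. Neither conflict depends on one: 45 mg against 30 mg, and interrupt against no change, read the same with or without them.

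**The case against.** **The 30-mg floor may be a deliberate exception for hypertension, with the 45-mg sentences belonging to the dermatologic and NIP tables they follow.** Nothing says so. Table 11-7 covers copanlisib-related adverse events without exception and has no 30-mg row. If an exception is meant, it has to be written.

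**The NIP text may describe a hold during work-up and the table the action after diagnosis.** That would reconcile them if the table covered only confirmed NIP, but its heading includes suspected NIP.

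**The guidance is discretionary.** This stands in part. An investigator may always be more cautious, so holding copanlisib at grade 1 would breach nothing. But discretion does not define a 30-mg level, and an investigator who follows the table still departs from the mandatory wording of the text.

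**The consequence is narrow.** This stands. It affects later infusions only. Section 11.2 also lets a patient who stops one drug continue the other, and vemurafenib has its own ladder in Table 11-5.

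Three stronger readings are tempting, and the documents do not support them:

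- *Table 11-9 footnote b implies a level below 45 mg*, because "re-escalation to dose level -1 or 1 is allowed, at the investigator's discretion" and level -1 in Table 11-7 is already the lowest. But Table 11-7 has levels 0 and -1 and no level 1, so the footnote does not fit that numbering. Under Table 9-1, levels -1 and 1 both carry copanlisib 45 mg and nothing lower follows. It is a numbering fault, not evidence for a lower dose.
- *Table 11-13 is a third conflict.* For asymptomatic glucose above 500 mg/dl it says "Will require dose reduction for subsequent treatment infusion" and names no floor. It contradicts nothing, because the general ladder supplies the floor.
- *The conflict changes DLT scoring and so the MTD.* The post-dose row of Table 11-12 is limited to drug-related hypertension not manageable despite optimal treatment. Item 1 of the DLT definition in Section 9.2 excepts grade 3 hypertension only if it was without optimal intervention or was transient. Such events, unless transient, are therefore already DLTs whichever floor applies. The reduction for hypertension during the infusion is discretionary, so it is not clearly the required, permanent reduction in item 4.

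**Conclusion.** Both contradictions stand in the current text, with high confidence. The copanlisib floor is 45 mg in six places and 30 mg in one, and the conflict can arise at the starting dose. Suspected grade 1 NIP carries two opposite actions. The general-guidelines sentence settles neither.

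The point rests on the clarity of the safety instructions and should be fixed. It does not question the validity of the MTD, and it claims no event rate or patient count. Its practical reach is patients with grade 3 hypertension on 45 mg, or with suspected grade 1 NIP, who would otherwise go on to the second infusion. This assumes the two-dose schedule of Section 4.2. Nothing here implies which dose or action is right.

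**What to change.** Amend Section 11.2 so that:

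1. one lowest copanlisib level applies across Tables 11-7 to 11-12, their footnotes and the adjoining text, or any exception for a particular toxicity is stated and entered in Table 11-7;
2. one action applies to suspected grade 1 NIP, in both the text and Table 11-11.

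The sponsor's clinicians decide which level and which action.

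Minor points for the same amendment:

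- Clarify the level numbering in footnote b to Table 11-9, which does not match Table 11-7.
- Align the hypertension text with Table 11-12. The text says that later doses should be reduced where the table says that they may be, and it says to interrupt the infusion where the table also allows slowing it.
- Correct the reference to a Table 8, which is not among the numbered tables.

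The cost is a protocol wording amendment, with no change to the sample size, the escalation rules or the analysis.

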12.0 CRITERIA FOR THERAPEUTIC RESPONSE/OUTCOME ASSESSMENT

For the purposes of this study, patients should be re-evaluated for response as per the study calendars in Section 10.0. Confirmatory scans for assessment of partial and complete responses should also be obtained no less than 4 weeks after initial documentation of objective response.

Response and progression will be evaluated using the new international criteria proposed by the revised RECIST guidelines (version 1.1)24, with some amendments, as indicated below for this protocol. Changes in the largest diameter (unidimensional measurement) of the tumor lesion and the shortest diameter, in the case of malignant lymph nodes, are included in RECIST 1.1.

Definitions

Evaluable for DLT: All patients will be evaluable for DLT from the time of their first treatment with vemurafenib and copanlisib.

Evaluable for toxicity: All patients will be evaluable for toxicity from the time of their first treatment with vemurafenib.

Evaluable for objective response: Please see Section 14 for guidelines regarding evaluable for response.

Evaluable Non-Target Disease Response: Patients who have lesions present at baseline that are evaluable but do not meet the definitions of measurable disease, have received at least one cycle of therapy, and have had their disease re-evaluated will be considered evaluable for non-target disease. The response assessment is based on the presence, absence, or unequivocal progression of the lesions.

Disease Parameters

Measurable disease: Measurable lesions are defined as those that can be accurately measured in at least one dimension (longest diameter to be recorded) as 20 mm by chest x-ray or as 10 mm with CT scan, MRI, or calipers by clinical exam. All tumor measurements must be recorded in millimeters (or decimal fractions of centimeters).

Note: Tumor lesions that are situated in a previously irradiated area might or might not be considered measurable. *If the investigator thinks it appropriate to include them, the conditions under which such lesions should be considered must be defined in the protocol.*

Malignant lymph nodes: To be considered pathologically enlarged and measurable, a lymph node must be 15 mm in short axis when assessed by CT scan (CT scan slice thickness recommended to be no greater than 5 mm). At baseline and in follow-up, only the short axis will be measured and followed.

Non-measurable disease: All other lesions (or sites of disease), including small lesions (longest diameter <10 mm or pathological lymph nodes with 2:10 to <15 mm short axis), are considered non-measurable disease. Bone lesions, leptomeningeal disease, ascites, pleural/pericardial effusions, lymphangitis cutis/pulmonitis, inflammatory breast disease, and abdominal masses (not followed by CT or MRI), are considered as non-measurable.

Note: Cystic lesions that meet the criteria for radiographically defined simple cysts should not be considered as malignant lesions (neither measurable nor non-measurable) since they are, by definition, simple cysts.

'Cystic lesions' thought to represent cystic metastases can be considered as measurable lesions, if they meet the definition of measurability described above. However, if non-cystic lesions are present in the same patient, these are preferred for selection as target lesions.

Target lesions: All measurable lesions up to a maximum of 2 lesions per organ and 5 lesions in total, representative of all involved organs, should be identified as **target lesions** and recorded and measured at baseline. Target lesions should be selected on the basis of their size (lesions with the longest diameter), be representative of all involved organs, but in addition should be those that lend themselves to reproducible repeated measurements. It may be the case that, on occasion, the largest lesion does not lend itself to reproducible measurement in which circumstance the next largest lesion which can be measured reproducibly should be selected. A sum of the diameters (longest for non-nodal lesions, short axis for nodal lesions) for all target lesions will be calculated and reported as the baseline sum diameters. If lymph nodes are to be included in the sum, then only the short axis is added into the sum. The baseline sum diameters will be used as reference to further characterize any objective tumor regression in the measurable dimension of the disease.

Non-target lesions: All other lesions (or sites of disease) including any measurable lesions over and above the 5 target lesions should be identified as **non-target lesions** and should also be recorded at baseline. Measurements of these lesions are not required, but the presence, absence, or in rare cases unequivocal progression of each should be noted throughout follow-up.

Methods for Evaluation of Measurable Disease

All measurements should be taken and recorded in metric notation using a ruler or calipers. All baseline evaluations should be performed as closely as possible to the beginning of treatment and never more than 4 weeks before the beginning of the study.

The same method of assessment and the same technique should be used to characterize each identified and reported lesion at baseline and during follow-up. Imaging-based evaluation is preferred to evaluation by clinical examination unless the lesion(s) being followed cannot be imaged but are assessable by clinical exam.

Clinical lesions: Clinical lesions will only be considered measurable when they are superficial (e.g., skin nodules and palpable lymph nodes) and 10 mm diameter as assessed using calipers (e.g., skin nodules). In the case of skin lesions, documentation by color photography, including a ruler to estimate the size of the lesion, is recommended.

Chest x-ray: Lesions on chest x-ray are acceptable as measurable lesions when they are clearly defined and surrounded by aerated lung. However, CT is preferable.

Conventional CT and MRI: This guideline has defined measurability of lesions on CT scan based on the assumption that CT slice thickness is 5 mm or less. If CT scans have slice thickness greater than 5 mm, the minimum size for a measurable lesion should be twice the slice thickness. ALL CTs SHOULD BE PERFORMED WITHOUT IODINATED CONTRAST.

MRI is also acceptable in certain situations (e.g. for body scans). Use of MRI remains a complex issue. MRI has excellent contrast, spatial, and temporal resolution; however, there are many image acquisition variables involved in MRI, which greatly impact image quality, lesion conspicuity, and measurement. Furthermore, the availability of MRI is variable globally. As with CT, if an MRI is performed, the technical specifications of the scanning sequences used should be optimized for the evaluation of the type and site of disease. Furthermore, as with CT, the modality used at follow-up should be the same as was used at baseline and the lesions should be measured/assessed on the same pulse sequence. It is beyond the scope of the RECIST guidelines to prescribe specific **MRI** pulse sequence parameters for all scanners, body parts, and diseases. Ideally, the same type of scanner should be used and the image acquisition protocol should be followed as closely as possible to prior scans. Body scans should be performed with breath-hold scanning techniques, if possible.

PET-CT: At present, the low dose or attenuation correction CT portion of a combined PET-CT is not always of optimal diagnostic CT quality for use with RECIST measurements. However, if the site can document that the CT performed as part of a PET-CT is of identical diagnostic quality to a diagnostic CT, then the CT portion of the PET-CT can be used for RECIST measurements and can be used interchangeably with conventional CT in accurately measuring cancer lesions over time. Note, however, that the PET portion of the CT introduces additional data which may bias an investigator if it is not routinely or serially performed.

Ultrasound: Ultrasound is not useful in assessment of lesion size and should not be used as a method of measurement. Ultrasound examinations cannot be reproduced in their entirety for independent review at a later date and, because they are operator dependent, it cannot be guaranteed that the same technique and measurements will be taken from one assessment to the next. If new lesions are identified by ultrasound in the course of the study, confirmation by CT or MRI is advised. If there is concern about radiation exposure at CT, MRI may be used instead of CT in selected instances.

Endoscopy, Laparoscopy: The utilization of these techniques for objective tumor evaluation is not advised. However, such techniques may be useful to confirm complete pathological response when biopsies are obtained or to determine relapse in trials where recurrence following complete response (CR) or surgical resection is an endpoint.

Cytology, Histology: These techniques can be used to differentiate between partial responses (PR) and complete responses (CR) in rare cases (e.g., residual lesions in tumor types, such as germ cell tumors, where known residual benign tumors can remain).

The cytological confirmation of the neoplastic origin of any effusion that appears or worsens during treatment when the measurable tumor has met criteria for response or stable disease is mandatory to differentiate between response or stable disease (an effusion may be a side effect of the treatment) and progressive disease.

FOG-PET: While FOG-PET response assessments need additional study, it is sometimes reasonable to incorporate the use of FOG-PET scanning to complement CT scanning in assessment of progression (particularly possible 'new' disease). New lesions on the basis of FOG-PET imaging can be identified according to the following algorithm:

- a. Negative FOG-PET at baseline, with a positive FOG-PET at follow-up is a sign of PD based on a new lesion.
- b. No FOG-PET at baseline and a positive FOG-PET at follow-up: If the positive FOG-PET at follow-up corresponds to a new site of disease confirmed by CT, this is PD. If the positive FOG-PET at follow-up is not confirmed as a new site of disease on CT, additional follow-up CT scans are needed to determine if there is truly progression occurring at that site (if so, the date of PD will be the date of the initial abnormal FOG-PET scan). If the positive FOG-PET at follow-up corresponds to a pre-existing site of disease on CT that is not progressing on the basis of the anatomic images, this is not PD.
- c. FOG-PET may be used to upgrade a response to a CR in a manner similar to a biopsy in cases where a residual radiographic abnormality is thought to represent fibrosis or scarring. The use of FOG-PET in this circumstance should be prospectively described in the protocol and supported by disease-specific medical literature for the indication. However, it must be acknowledged that both approaches may lead to false positive CR due to limitations of FOG-PET and biopsy resolution/sensitivity.

Note: A 'positive' FOG-PET scan lesion means one which is FOG avid with an uptake greater than twice that of the surrounding tissue on the attenuation corrected image.

Response Criteria

Evaluation of Target Lesions:

Complete Response (CR): Disappearance of all target lesions. Any pathological lymph nodes (whether target or non-target) must have reduction in short axis to <10 mm.

Partial Response (PR): At least a 30% decrease in the sum of the diameters of target lesions, taking as reference the baseline sum diameters.

Progressive Disease (PD): At least a 20% increase in the sum of the diameters of target lesions, taking as reference the smallest sum on study (this includes the baseline sum if that is the smallest on study). In addition to the relative increase of 20%, the sum must also demonstrate an absolute increase of at least 5 mm. (Note: the appearance of one or more new lesions is also considered progressions).

Stable Disease (SD): Neither sufficient shrinkage to qualify for PR nor sufficient increase to qualify for PD, taking as reference the smallest sum diameters while on study.

Evaluation of Non-Target Lesions:

Complete Response (CR): Disappearance of all non-target lesions and normalization of tumor marker level. All lymph nodes must be non-pathological in size (<10 mm short axis).

Note: If tumor markers are initially above the upper normal limit, they must normalize for a patient to be considered in complete clinical response.

Non-CR/Non-PD: Persistence of one or more non-target lesion(s) and/or maintenance of tumor marker level above the normal limits.

Progressive Disease (PD): Appearance of one or more new lesions and/or *unequivocal progression* of existing non-target lesions. *Unequivocal progression* should not normally trump target lesion status. It must be representative of overall disease status change, not a single lesion increase.

Although a clear progression of "non-target" lesions only is exceptional, the opinion of the treating physician should prevail in such circumstances, and the progression status should be confirmed at a later time by the review panel (or Principal Investigator).

Evaluation of Best Overall Response:

The best overall response is the best response recorded from the start of the treatment until disease progression/recurrence (taking as reference for progressive disease the smallest measurements recorded since the treatment started). The patient's best response assignment will depend on the achievement of both measurement and confirmation criteria.

For Patients with Measurable Disease (i.e., Target Disease)

Target Lesions	Non-Target Lesions	New Lesions	Overall Response	Best Overall Response when Confirmation is Required*
CR	CR	No	CR	... 4 wks. Confirmation**
CR	Non-CR/Non-PD	No	PR	
CR	Not evaluated	No	PR	
PR	Non-CR/Non-PD/not evaluated	No	PR	... 4 wks. Confirmation**
SD	Non-CR/Non-PD/not evaluated	No	SD	Documented atleast once ... 4 wks. from baseline**
PD	Any	Yes or No	PD	
Any	PD***	Yes or No	PD	no prior SD, PR or CR
Any	Any	Yes	PD	

See RECIST 1.1 manuscript for further details on what is evidence of a new lesion.
 only for non-randomized trials with response as primary endpoint.

*** In exceptional circumstances, unequivocal progression in non-target lesions maybe accepted as disease progression.

...> patients with a global deterioration of health status requiring discontinuation of treatment without objective evidence of disease progression at that time should be reported as "symptomatic deterioration." Every effort should be made to document the objective progression even after discontinuation of treatment.

For Patients with Non-Measurable Disease (i.e., Non-Target Disease)

Non-Target Lesions	New Lesions	Overall Response
CR	No	CR
Non-CR/non-PD	No	Non-CR/non-PD*
Not all evaluated	No	not evaluated
Unequivocal PD	Yes or No	PD
Any	Yes	PD

'Non-CR/non-PD' is preferred over 'stable disease' for non-target disease since SD is increasingly used as an endpoint for assessment of efficacy in some trials so to assign this category when no lesions can be measured is not advised

NOTE: Patients with clinical and/or radiographic evidence of disease progression (as described above) on assessments performed before the 6-month evaluation post-vemurafenib and copanlisib plus 1-131 evaluation (i.e. on scans and/or evaluations performed prior to the evaluation scheduled for 6 months after therapeutic 1-131 is co-administered with vemurafenib/copanlisib) will be allowed to continue on study treatment and will be assessed as mandated by the protocol, if deemed clinically reasonable by the treating physician. For these patients, the final objective response assessment will be based on a comparison between the 6-month post-vemurafenib plus ^{131}I radiologic scan(s)/evaluations and the baseline, pretreatment radiologic scans.

PFS

PFS is defined as the duration of time from start of treatment (initiation of vemurafenib) to time of progression or death, whichever occurs first.

